6.10 Compliance

As outlined in section 6.1, all analysis will be conducted on an intent-to-treat basis. This means that overall compliance for the purposes of the efficacy study will be met when young people have been randomised and allocated into the treatment or control group.

However, we acknowledge that intent-to-treat analysis may underestimate the efficacy of the intervention if some boys in either trial arm do not adhere to their assigned treatment. To examine this, we will conduct Complier Average Causal Effect (CACE) analysis, which will indicate treatment effects amongst those who comply with the intervention. However, any analysis of treatment effects in the presence of non-compliance will also be exploratory. This will be estimated using two stage least squares (2SLS) regression (Gerber and Green, 2012), which uses the following two stages:

- 1. The first stage will model the compliance variable (i.e. number of sessions) using the same explanatory variables used for the primary analysis. This will be a logistic regression model used to generate predicted compliance.
- 2. The second stage models will use predicted compliance in place of the allocation group variable in the ITT primary analysis specified in section 6.2 to generate the CACE estimates.

We will report the results from the first stage of the 2SLS, along with the correlation between the instrument and endogenous variable and the associated F-test. Interpretations of the CACE estimates will be provided in the final report.

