	6.1	Overview	12		
	6.2	Primary outcome analysis	13		
	6.3	Secondary outcomes analysis	14		
	6.4	Subgroup analyses	16		
	6.5	Further analyses	17		
	6.6	Interim analyses and stopping rules	18		
	6.7	Longitudinal follow-up analyses	19		
	6.8	Imbalance at baseline	19		
	6.9	Missing data	20		
	6.10	Compliance	21		
	6.11	Intra-cluster correlations (ICCs)	22		
	6.12	Presentation of outcomes	22		
7	Ref	erences	23		

3 Introduction

This is the statistical analysis plan for an efficacy study, two-arm parallel randomised control trial (RCT) evaluation and implementation and process evaluation (IPE) of Future Men's Boys Development Programme (BDP). The BDP will be delivered across six schools in South London between September 2023 and July 2025 i.e. across two academic years. The efficacy study will run until March 2026.

The BDP is a targeted, manualised, social and emotional learning programme delivered across 12 one-to-one, 50 to 60-minute-long sessions. It aims to develop the social and emotional capacity and skills of boys in Years 7-11 who are at risk of exclusion and disengagement from schools, to improve school engagement and reduce the likelihood of exclusion.

The evaluation team are collecting a range of data throughout the trial. This includes:

- Self-reported outcomes measures, including the School Connectedness Questionnaire, the Strengths and Difficulties Questionnaire, and the Social Support and Rejection Scale.
- Demographic data provided by school partners, including age, sex, Free School Meal (FSM) eligibility, special educational needs and disabilities (SEND) data, English as an Additional Language (EAL) and care status.
- Activity and monitoring data collected by the Future Men delivery team.

This document sets out our planned analysis for each data type in more detail. The rest of this document is structured in the following way:

- Section 4: Trial design sets out the research questions, key outcomes and measures, and randomisation approach for the trial.
- Section 5: Sample size calculations presents the power calculations for the trial.
- Section 6: Analysis sets out the approach to analysis of primary outcomes, secondary outcomes, subgroup analysis, longitudinal analysis, further and interim analysis, missing data, compliance and outcomes presentation.

4 Trial design

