6.5 Further analyses

We will conduct the following exploratory further analysis:

• The impact of positive relationships. We will evaluate the extent to which positive relationships between the young person and project co-ordinator (treatment group) or significant adult (control group) influenced the primary outcome over and above the impact of the BDP through the SSRS. We are proposing conducting this analysis because the theory of change suggests that the key mechanism of change for the BDP is that it has its effect through an increase in positive relationships with a trusted adult. This will take a mediation analysis approach, i.e. we will estimate the direct and indirect effects, following the approach outlined in Gunzler et al. (2013).

About the Social Support and Rejection Scale

The SSRS has 4 dimensions: Feels valued, trust, mentoring, and negativity. Each item is scored from 1 (never) to 5 (always). Each subscale score is the average of items that make up the subscale. Higher scores on the negativity scale reflect higher levels of stress and negativity within the relationship. For the overall scoring of the scale a high score represents a positive relationship.

• Improvements to school attendance and reductions to exclusion as measured by school administrative data. If we are able to access school administrative data which is of sufficient high quality, consistency and comparability across schools, we will explore whether there is a difference in attendance and exclusions between those in

the BDP group and those in the business-as-usual group. This will follow the same model as set out for the primary and secondary outcomes analysis.

• **Dosage and fidelity.** Any analysis relating to dosage and fidelity will be exploratory in nature. If power calculations suggest that the analysis will be sufficiently powered, we will explore the association between the level of dosage and the impact on the SCQ. This data will be captured by monitoring data on number of sessions received collected by the Future Men delivery team. This analysis will be conducted using a general linear model assuming normality, or a generalized linear model. It will answer questions such as: does attending 8 or more BDP sessions result in a similar impact as attending all 12 sessions?

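### The CACE analysis is called 2SLS but specifies a logistic first stage for a session count, with no cut-off and a second definition of compliance, so its steps cannot all be followed

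*SAP*

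**What the plan says.** SAP section 6.10 names two-stage least squares as the estimator of the CACE and labels the analysis exploratory. It then sets out two stages.

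- Stage 1: "The first stage will model the compliance variable (i.e. number of sessions) using the same explanatory variables used for the primary analysis". The next sentence fixes the model: "This will be a logistic regression model used to generate predicted compliance".
- Stage 2: "The second stage models will use predicted compliance in place of the allocation group variable in the ITT primary analysis specified in section 6.2".
- Reporting: the first-stage results, "along with the correlation between the instrument and endogenous variable and the associated F-test".

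The opening of the same section gives another meaning of compliance: "overall compliance for the purposes of the efficacy study will be met when young people have been randomised and allocated".

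The programme is "delivered across 12 one-to-one, 50 to 60-minute-long sessions" (section 3), so the count runs from 0 to 12. Section 6.10 gives no threshold that turns the count into complier or non-complier. The only cut-off in the SAP is an example dosage question in section 6.5: "does attending 8 or more BDP sessions result in a similar impact as attending all 12 sessions". The SAP does not say how second-stage standard errors will be obtained.

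**The concern.** The listed steps do not fit together. The outcome of the first stage is a count, the model is for a binary outcome, and the named method requires a least-squares first stage. An analyst must change at least one of these to produce a result, and the choice decides what is estimated: an effect per session, or an effect in boys above some cut.

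Section 6.1 says the syntax will be developed after all data have been collected, so that choice may be made with outcomes in hand. This is the SAP's only planned instrumental-variable estimate of the effect of receiving the programme. The dosage analysis in section 6.5 is an association, and it is conditional on power.

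**Working it through.** Section 6.10 states no figure, so there is none to reproduce. The check has a reading step and a simulation step.

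**1. Variable against model.** The count runs from 0 to 12. A binary logistic model needs an outcome between 0 and 1, and a trial fit to a simulated count was rejected by the software for that reason. An ordinal or grouped-binomial logit would accept the count, but the SAP names neither.

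**2. Dichotomised version.** Let D = 1 if sessions reach a cut. The first stage is logit P(D = 1) = a0 + a1·Baseline + a2·Group + school terms. If no control boy attends, P(D = 1 | Group = 0) = 0, which needs a2 → ∞: the data are separated. A trial fit with a cut of 8 did not converge (a2 about 27, SE about 35,600). That coefficient is part of the first stage the SAP promises to report.

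**3. Estimator.** 2SLS regresses D linearly on Group, baseline and school. Its variance uses the residual Y − Xβ with the observed D. Running the section 6.2 model on predicted compliance uses the residual from the predicted D instead, which is an OLS and not an IV standard error. With logistic predictions, consistency also leans on the logistic form being right.

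**4. F-test.** A logistic fit gives chi-square tests. An F for the instrument comes from a linear regression of compliance on Group and covariates. In one simulated trial this F was about 230 for the binary indicator and about 1,460 for the count (illustrative only).

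**5. Size of the numerical harm.**
- Inputs from the SAP: 424 boys at follow-up (212 per arm) and pre/post correlation 0.7 (section 5.2), six schools, sessions 0 to 12.
- Assumptions: cut at 8; effect of 0.35 or 0.80 SD only in boys reaching the cut; 0 or 10% of control boys attending; attendance depending on school, an unmeasured factor related to outcome (loading 0.5 or 0.8 on the outcome residual), and baseline, linearly or through its square. There were ten scenarios with 1,500 trials each.
- With no control attendance, the plug-in used the limit of the separated fit: 0 for controls, and a logistic fit within the BDP arm.

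Four of the ten scenarios (loading 0.5):

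| Control attendance; baseline form; true effect | Linear 2SLS: mean, mean IV SE, coverage | Logistic plug-in: mean, sampling SD, mean OLS SE, coverage |
|---|---|---|
| 0%; linear; 0.35 | 0.348, 0.132, 94.5% | 0.356, 0.122, 0.122, 95.1% |
| 10%; linear; 0.35 | 0.353, 0.148, 95.5% | 0.369, 0.134, 0.142, 96.2% |
| 10%; linear; 0.80 | 0.802, 0.148, 95.5% | 0.831, 0.137, 0.155, 97.3% |
| 0%; square; 0.80 | 0.796, 0.148, 96.1% | 0.807, 0.139, 0.164, 98.0% |

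Across all ten:
- Plug-in means were about 1 to 5% above the truth (largest 0.369/0.35 = 1.05).
- The plug-in SE ran from equal to the sampling SD (0.122/0.122) to about 18% above it (0.164/0.139 = 1.18).
- Plug-in coverage was 95.1 to 98.0%. Linear 2SLS coverage was 94.4 to 96.1%.

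**6. What the coding decides.** In the first row, 2SLS on the count gave 0.0249 SD per session, or 12 × 0.0249 = 0.299 SD for 12 sessions, against 0.348 from the binary indicator in the same simulated trials. These are different quantities, and section 6.10 does not say which is wanted.

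**The case against.** The strongest defence is that little harm follows. The analysis is exploratory and the ITT result does not depend on it. What stands of this, and of three stronger readings that a reader might infer, is as follows.

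- *That the analysis would fail to run.* Only the binary fit to the raw count fails. Once sessions are dichotomised, the second stage needs only the predictions, and these stay well defined under separation: near 0 in controls, fitted probabilities in the BDP arm. In a further simulation the plug-in returned an estimate in 800 of 800 trials. Separation itself assumes no control attendance, and section 6.10 allows for non-adherence in either arm.
- *That there would be no valid standard errors or F-test.* The SAP is silent on standard errors, and the uncorrected ones were close or conservative in most settings. Two further simulations with a cut of 8 gave a plug-in of 0.241 against linear IV 0.244 (mean SE 0.084, SD 0.081), and 0.269 against 0.271 (0.096, 0.097). An F-test is obtainable from a separate linear regression; the SAP does not specify one.
- *That the CACE would be inflated by partial attenders.* A simulation with an effect linear in sessions and a cut of 8 gave 0.277 against a true 0.220, about 26% too large (0.277/0.220 = 1.26). This does not measure the logistic defect. Section 6.10 sets no such cut, and the bias remains under a linear first stage. It disappears if only boys above the cut benefit (0.274 against 0.280).

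Nor do the documents show that the choice will be improvised after unblinding. Section 6.1 also promises to finalise the plan before follow-up outcomes are collected, though it does not say that section 6.10 will be settled then.

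The contradiction between variable, model and named method stands, because it needs none of these assumptions.

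**Conclusion.** The point holds as a specification error in an exploratory analysis. As written, section 6.10 combines a 0-to-12 count, a binary-outcome model, a method that requires a linear first stage, and a second definition of compliance under which every allocated boy complies. These cannot all be followed. The plug-in is not 2SLS, its second-stage standard errors are not IV standard errors, and the promised F-test needs a regression that is not described.

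The numerical effect on the estimate and its standard error was small in the scenarios tested. That rests on assumed attendance, confounding, effect sizes and a cut of 8, none of which section 6.10 provides. The more practical consequence is that the estimand is left open between a per-session effect and an effect above an unstated cut. The contradiction and the open estimand follow from the text alone. The primary ITT analysis is unaffected.

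**What to change.** Rewrite the two stages in section 6.10:

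- Name one compliance variable, either the session count or a defined binary indicator, and reconcile it with the section's statement that compliance is met on allocation.
- Replace stage 1 with a linear (OLS) regression of that variable on Group, the baseline score and school.
- Fit both stages in one 2SLS/IV routine with Group as the instrument and IV standard errors.
- Report that first stage's F and partial R², with the correlation already promised.
- If the count is used, report the effect per session and state the linear dose-response assumption behind any scaling to 12 sessions.
- If a binary cut is used, state that the exclusion restriction then assumes no effect of sessions below the cut.

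The cost is one paragraph of SAP wording, best settled before outcomes are examined. It needs no new data, because section 6.5 already has session numbers recorded in the monitoring data. SPSS, the package named in section 6.1, has a two-stage least-squares procedure.

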6.11 Intra-cluster correlations (ICCs)

This is not a clustered randomised controlled trial. As such, ICCs will not be calculated.

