5.2 Whole cohort

We have determined the overall sample size for the trial a priori, in line with YEF guidance. These calculations suggest that a final sample size of 422 (211 per group) would ensure that the efficacy study is sufficiently powered to detect a statistically significant result if it exists (power = 0.80, two tailed, p < 0.05). Please note that our planned sample size for the trial is 480 boys, in line with Future Men's capacity to deliver the intervention. This provides buffer for attrition throughout the trial of 12% (58 boys). However, the final sample for the trial will not be finalised until randomisation is complete in April 2025. We will update Table 2 with

the final figures once they are known. Our approach to estimating the sample size for this efficacy study is conservative and has been influenced by the following:

- **YEF guidance.** YEF guidance suggests that efficacy study RCTs should have a Minimum Detectable Effect Size (MDES) of 0.20.
- Available data on the School Connectedness Questionnaire. The primary outcome measure for the study is school engagement, as measured by Marsh and Randolph's (2020) School Connectedness Questionnaire. In their validation study, Marsh and Randolph (2020) reported mean average scores, standard deviations and skew for each of the three SCQ sub-scales across two samples one for a sample of young people in general education, and one for a sample for young people experiencing emotional and behavioural disorders. Total scores and the associated standard deviation were not reported in Marsh and Randolph's (2020) paper, and data on pretest and post-test correlations has also not been published. As such, we have drawn from available data on similar measures (see below).
- Available data on similar measures. As described above, pre-test post-test correlations for the SCQ have not been published. Therefore, we draw from available data on the Student Engagement in Schools Questionnaire (Lam et al., 2014, p.38). For this scale, six month test-retest results were found to be 0.73 for the full-scale. In line with our conservative approach, we have therefore suggested a pre-test/post-test correlation of 0.7.

[figure not shown]

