Table 2 at the start of this section presents power calculations which have been conducted in line with the above approach. These power calculations suggest that a sample size of 211 in each group (i.e. 422 in total) will be sufficiently powered to detect a statistically significant result if it exists (power = 0.80, two tailed, MDES = 0.195).³

[figure not shown]
Future Men's delivery capacity enables them to deliver the BDP intervention to a maximum of 240 boys over the duration of the study. With a control group allocated as close as is feasible to a one-to-one ratio, this means a total sample size of 480 boys is achievable under existing plans. Based on the power calculation above, this means even with attrition or non-completion of questionnaires for 38 boys (12%, which is slightly above YEF's desired target of no more than 10% attrition) the sample should be able to detect statistically significant differences if they exist.

³ These power calculations have been conducted using PowerUp. Available here: https://www.causalevaluation.org/power-analysis.html [Last accessed 17/06/2024].

Update: March 2025

Baseline data collection was completed in February 2025, with 483 baseline surveys collected (i.e, 3 more than our target of 480). Of these, 243 boys are in the BDP group, and 240 are in the signposting group, which is in line with our 1:1 allocation ratio target. The CONSORT diagram below presents this in more detail.

Maintaining the above assumptions of a 12% attrition rate, this suggests that the trial will have a final sample of 425 questionnaires at T2. Rounded down to 424 (i.e. 212 in each group), power calculations suggest that this will result in a final MDES of 0.195.

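### Section 6.11's reason for not calculating ICCs does not cover clustering by delivering co-ordinator in the BDP arm, so the section 6.2 standard error, p-value and stated MDES may be too optimistic

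*SAP*

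**What the plan says.** Section 6.11 consists of one argument: "This is not a clustered randomised controlled trial. As such, ICCs will not be calculated". Section 4.1 confirms individual randomisation stratified by school. The section 6.2 primary model contains baseline, allocation group, school dummies and a single error term with constant variance. It has no co-ordinator term, and no sensitivity analysis elsewhere in the SAP concerns co-ordinators.

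On delivery, the Introduction describes a manualised "social and emotional learning programme delivered across 12 one-to-one" sessions. Section 4.3 refers to data collection by a co-ordinator who is not delivering support, which implies that other co-ordinators do deliver. The footnote to Table 1 says that a boy will not have worked with the co-ordinator before the BDP. Sections 6.3 and 6.5 measure the relationship with the co-ordinator in the treatment arm and with a significant adult in the control arm. Section 6.5 says of the BDP's key mechanism that "it has its effect through an increase in positive relationships with a trusted adult".

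On sample size, section 5.2 uses "power = 0.80, two tailed, p < 0.05", and for the correlation it says "we have therefore suggested a pre-test/post-test correlation of 0.7". It concludes that "a sample size of 211 in each group (i.e. 422 in total") suffices ("power = 0.80, two tailed, MDES = 0.195"). The March 2025 update says: "Rounded down to 424 (i.e. 212 in each group), power calculations suggest that this will result in a final MDES of 0.195". Table 2 marks the cluster-level pre/post correlation as not applicable.

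**The concern.** The unit of randomisation settles how allocation was made. It does not settle whether outcomes are independent after treatment. Boys in the BDP arm who share a co-ordinator may share part of their outcome if some co-ordinators are more effective than others. Controls have no matching grouping, so the design is partially nested.

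School dummies remove what both arms of a school have in common. A co-ordinator effect that acts only on BDP boys stays in the within-school difference between arms, which is the quantity that beta_2 estimates.

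At stake are the standard error and p-value of the primary effect, and the claim that the trial can detect 0.195. Section 5.2 cites a funder target of 0.20, so the margin is only 0.005. With ICCs ruled out, a reader of the final report could not tell whether the issue arose.

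**Working it through.** **Inputs from the SAP.** Two-sided alpha 0.05; power 0.80; pre/post correlation 0.7, so the residual variance is 1 − 0.49 = 0.51; 212 boys per arm analysed (section 5.2 update).

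**Inputs assumed.** The SAP gives no number of co-ordinators, caseload or ICC. I take c = 4, 6, 8 or 12 co-ordinators with equal caseloads m = 212/c, and a co-ordinator ICC of 0.01, 0.02 or 0.05 on the baseline-adjusted residual scale, in the BDP arm only.

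**Step 1: the plan's own figure.** MDES = (t₀.₉₇₅ + t₀.₈₀) × √(0.51 / (0.25 N)), where the sum of the t values is about 2.81.
- N = 422: 0.1952.
- N = 424: 0.1948.

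Both round to the stated 0.195. The calculation contains no term for deliverer clustering.

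**Step 2: partially nested variance.** The BDP-arm design effect is DE = 1 + (m − 1) × ICC. The control arm has 1. The variance of the difference is multiplied by (DE + 1)/2, and the standard error by its square root.

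Example with c = 6 and ICC 0.05: m = 35.3; DE = 1 + 34.3 × 0.05 = 2.72; variance factor (2.72 + 1)/2 = 1.86; SE factor 1.36; MDES 0.1948 × 1.363 = 0.266.

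Each cell gives the values for ICC 0.01 / 0.02 / 0.05:

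| Co-ordinators (caseload) | SE factor | MDES | Power at 0.195 (%) | Coverage of nominal 95% ANCOVA interval (%) |
|---|---|---|---|---|
| 4 (53.0) | 1.12 / 1.23 / 1.52 | 0.219 / 0.240 / 0.295 | 71 / 63 / 46 | 91.9 / 88.8 / 80.4 |
| 6 (35.3) | 1.08 / 1.16 / 1.36 | 0.211 / 0.226 / 0.266 | 74 / 68 / 54 | 93.0 / 90.9 / 85.0 |
| 8 (26.5) | 1.06 / 1.12 / 1.28 | 0.207 / 0.218 / 0.249 | 75 / 71 / 59 | 93.5 / 92.0 / 87.4 |
| 12 (17.7) | 1.04 / 1.08 / 1.19 | 0.203 / 0.210 / 0.232 | 77 / 74 / 66 | 94.0 / 93.0 / 90.0 |

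The true standard error is thus 4% to 52% larger than the ANCOVA one. Put the other way, the reported one is 1 − 1/1.04 to 1 − 1/1.52, or about 4% to 34%, too small.

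**Step 3: do school dummies help?** The section 6.2 model was simulated with six schools, 36 boys per arm per school, no average effect and 3,000 runs per setting. The rejection rates at a nominal 5% were:

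| ICC | One co-ordinator per school | Two per school |
|---|---|---|
| 0 | 5.2% | 5.0% |
| 0.02 | 8.5% | 7.5% |
| 0.05 | 15.3% | 10.3% |

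The excess appears only when the co-ordinator effect is present, and the school dummies do not remove it.

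**Step 4: the section 6.12 interval.** The standard error formula in footnote 8 uses only the arm sizes and g. At 212 per arm and g = 0.195 it is √(424/212² + 0.195²/848) = 0.0974. The ANCOVA standard error is √(2 × 0.51/212) = 0.0694. The ratio is 1.40 and the variance ratio 1.97. This interval is therefore about 1.4 times too wide when there is no clustering. It becomes too narrow only when (DE + 1)/2 exceeds 1.97, that is, when ICC × (m − 1) exceeds about 1.94. Of the 12 scenarios only c = 4 with ICC 0.05 does so (52 × 0.05 = 2.60). The next highest, c = 6 with ICC 0.05, gives 1.72.

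**The case against.** Much of the case on the other side stands.

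- **Clustering is not ignored altogether.** A reader might infer that 6.11 dismisses every form of it. It does not: school is the stratifier and is in the primary model. The statement that the trial is not cluster randomised is also true. The gap is the co-ordinator within the BDP arm.
- **The reported interval need not be too narrow.** A reader might infer that the primary confidence interval is too short. For the Hedges' g interval of section 6.12, step 4 shows the reverse in 11 of 12 scenarios. But that width comes from leaving out the baseline adjustment. It is an accidental offset, and it does not protect the ANCOVA p-value or the interval for beta_2.
- **The SAP does not say that co-ordinators differ.** A mechanism that works through a relationship does not by itself imply variation between deliverers, and a manualised one-to-one programme may limit it. Delivery by co-ordinator is a sound inference, not a stated fact. The SAP does not say whether a boy keeps one co-ordinator, or who does the signposting for controls. Section 4.3 also attaches the co-ordinator to the control arm, against sections 6.3 and 6.5; it looks like a slip.
- **The target of inference matters.** Conditional on the co-ordinators in this trial, the ANCOVA interval is not too narrow for this reason. If the BDP changed no boy's outcome, there would be no co-ordinator variance and no excess type I error. The rates in step 3 refer to a zero average effect over a wider set of co-ordinators. Section 4.2 asks whether the BDP can work in ideal circumstances, which favours the narrow reading. Section 6.1 justifies the analysis for those who might roll the programme out, which favours the wider one.
- **With few co-ordinators the variance component is poorly estimated.** This is true, and it is why the extra model should be a sensitivity analysis only.

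**Conclusion.** The reason given in 6.11 is insufficient, and nothing else in the SAP fills the gap. If co-ordinators differ, the section 6.2 standard error and p-value for beta_2 are too optimistic for inference beyond the trial's own co-ordinators, and the MDES of 0.195 holds only without such clustering.

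The range in step 2 rests wholly on the assumed 4 to 12 co-ordinators, equal caseloads and a residual ICC of 0.01 to 0.05. An ICC near zero would leave the plan's figures intact. The documents therefore do not support the stronger conclusion that the trial is underpowered or that its primary analysis is invalid. They support a correction to the reasoning and one inexpensive check.

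**What to change.** 1. Replace the reason in 6.11: individual randomisation removes the need for a cluster-randomised analysis, but clustering by delivering co-ordinator in the BDP arm will be examined.
2. Link each BDP boy to his delivering co-ordinator, and state how boys with more than one will be coded.
3. Report the co-ordinator ICC in the BDP arm with its interval, estimated with school effects in the model.
4. Pre-specify one sensitivity analysis of the primary outcome: a partially nested mixed model with the section 6.2 terms, a random co-ordinator effect in the BDP arm only, arm-specific residual variances and small-sample degrees of freedom.
5. Keep the ANCOVA as the headline and show both estimates and intervals side by side. Do not make the conclusion depend on an undefined rule that the two must agree.
6. State in section 5 that the MDES assumes no co-ordinator clustering.

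Section 6.1 already promises a finalised plan, and this belongs there, fixed before outcomes are compared by arm. The cost is a co-ordinator identifier from the delivery team, which already records sessions, and one further model in SPSS. The downside is that with few co-ordinators the ICC will be imprecise and the sensitivity interval wide. With only one co-ordinator per school, the co-ordinator effect cannot be told apart from a treatment effect that varies by school, and the report should say so.
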